9.1. Participant Compensation

Participants will be compensated \$50 for each protocol-specified clinic visit during the study.

Participants will typically receive these amounts at the end of each clinic visit. For completing all required study visits, participants will be compensated a minimum of \$300 and a maximum of \$600 due to additional study visits that may be required for some participants.

9.2. Participant Withdrawal

Participation in the study is voluntary, and a participant may withdraw at any time. For participants who withdraw, their data will be used up until the time of withdrawal.

9.3. Confidentiality

For security and confidentiality purposes, participants will be assigned an identifier that will be used instead of their name. Protected health information gathered for this study will be shared with the coordinating center, the Jaeb Center for Health Research in Tampa, FL. De-identified participant information may be provided to research sites involved in the study.

1084 CHAPTER 10: STATISTICAL CONSIDERATIONS

1085

1086 10.1. Statistical and Analytical Plans

1087 The approach to sample size and statistical analyses are summarized below. A detailed statistical
1088 analysis plan will be written and finalized prior to the completion of the study. The analysis plan
1089 synopsis in this chapter contains the framework of the anticipated final analysis plan.

1090 10.2. Statistical Hypotheses

- 1092 Null hypothesis: There will be no difference in percentage of CGM-measured glucose values
1093 <70 mg/dL between PLGS and SAP
- 1094 Alternate hypothesis: PLGS will improve the percentage of CGM-measured glucose values <70
1095 mg/dL over SAP.

1096 10.3. Sample Size

1097 Data from the JDRF Continuous Glucose Monitoring Randomized Clinical Trial was used to estimate
1098 SD and the frequency of time <70 mg/dL for the pump or MDI population. Assuming a crossover
1099 design with two 3 weeks periods, a 2-tailed test, a 33% relative reduction in 24-hour time <70 mg/dL,
1100 standard deviation of the paired differences = 3%, a type I error = 5%, and 90% power; a sample of 52
1101 participants is required.

1102 With a sample size of 90 participants, the primary analysis will have 99% power. The larger sample
1103 size will provide increased precision for safety analyses and subgroup analyses.

1104 10.4. Outcome Measures

1105 Primary Efficacy Endpoint:

- 1106 Percentage of sensor glucose values <70 mg/dL

1107 Secondary Efficacy Endpoints:

1108 *Hypoglycemia*

- 1109 Percentage of values <60 mg/dL
- 1110 Percentage of values <50 mg/dL
- 1111 AUC <70 mg/dL
- 1112 Low blood glucose index
- 1113 Frequency of CGM-measured hypoglycemic events (see below):

1114 *Glucose Control*

- 1115 Mean glucose
- 1116 Percentage of values 70 to 180 mg/dL

1117 *Hyperglycemia*

- 1118 Percentage of values >250 mg/dL
- 1119 Percentage of values >180 mg/dL
- 1120 AUC glucose >180 mg/dL
- 1121 High blood glucose index

1122 Each of the metrics listed will be calculated over 24 hours and separately for daytime (6am – 10pm)
1123 and nighttime (10pm – 6am). Secondary outcomes will also include the percentage of sensor glucose
1124 values <70 mg/dL calculated separately for daytime and nighttime.

1131
1132 A CGM-measured hypoglycemic event will be defined as at least 2 sensor values <54 mg/dl that are 15
1133 or more minutes apart plus no intervening values >54 mg/dl; at least 2 sensor values >70 mg/dl that are
1134 30 or more minutes apart with no intervening values <70 mg/dl, are required to define the end of an
1135 event, at which point the study participant becomes eligible for a new event..
1136

1137 **10.5. Description of Statistical Methods**
1138 **10.5.1. General Approach**
1139 This is a crossover study where each participant is randomized to treatment order. All analyses will
1140 compare the 3-week period of PLGS to the 3 week period of SAP and will follow the intention-to-treat
1141 principle with each period analyzed according to the treatment assigned by randomization regardless of
1142 actual PLGS utilization. All participants who have at least one CGM reading in each 3-week period
1143 will be analyzed. All p-values will be two-sided.
1144

1145 **10.5.2. Analysis Cohorts**
1146 • All randomized participants who have at least one CGM reading in each 3-week period will
1147 be analyzed for the Intention-to-Treat (ITT) Analysis.
1148 • Safety outcomes will be reported for all enrolled participants, irrespective of whether the
1149 study was completed.
1150 • A per-protocol analysis restricted to participants with at least 200 hours of CGM data in
1151 each 3 week period will also be conducted provided that there are at least 5 participants
1152 with less than 200 hours of CGM data in both treatment periods.
1153

1154 **10.6. Analysis of the Primary Efficacy Endpoint**
1155 The percentage of sensor glucose values <70 mg/dL will be calculated for each participant in each 3-
1156 week treatment period by pooling all sensor glucose readings that occur within each 3-week period. All
1157 sensor glucose readings will be weighted equally in the pooled percentages regardless of how they
1158 distribute across weeks. The percentage in the PLGS period will then be compared to the percentage in
1159 the SAP period for the same participant.
1160

1161 Summary statistics appropriate to the distribution will be calculated for % time below <70 mg/dL
1162 separately by treatment arm. A repeated measures regression model with an unstructured covariance
1163 structure will be fit for percent time below <70 mg/dL to compare the two treatments. The
1164 model will adjust for period as a covariate. If residual values from the regression model have a skewed
1165 distribution then an appropriate transformation or a nonparametric analysis based on ranks will be
1166 performed.
1167

1168 There will be no imputation of missing CGM data.
1169

1170 **10.7. Analysis of the Secondary Endpoints**
1171 Analysis of the secondary endpoints and additional CGM metrics will parallel the analysis of the
1172 primary endpoint above.
1173

1174 **10.8. Safety Analyses**
1175 The following safety outcomes will be tabulated by participant within each 3-week treatment period.
1176 The summary statistics will include start date, stop date, severity, relationship, resolution, and duration.

- Diabetic ketoacidosis (DKA), as defined by the Diabetes Control and Complications Trial (DCCT).
- Severe clinical hypoglycemic events such that the participant required assistance from another person to actively administer carbohydrate, glucagon, or engage in other resuscitative actions; note severe hypoglycemia could be considered both and efficacy and safety outcome
- Ketosis events (blood ketone level >1.0 mmol/L)
- All other reported adverse events
- Unanticipated adverse device effects

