58 may be randomized into the crossover trial. Immediately after randomization, subjects will enter the two
59 3-week study periods (21 days each) and will test one intervention per study period, using either the
60 PLGS or SAP system first. The interventions will not be separated by a washout period.
61

62 **2. Statistical Hypotheses**

- 63 • *Null Hypothesis*: There is no difference in the mean time spent below 70 mg/dL over the 21-day
64 period between the two treatment groups.
- 65 • *Alternative Hypothesis*: There is a nonzero difference in the mean time spent below 70 mg/dL
66 over the 21-day period between the two treatment groups.
67

68 **3. Sample Size**

69 The study is projected to include at least 90 subjects. Of these study participants, at least 45 will be $<$ 18
70 years old, and at least 45 will be \geq 18 years old. Of the 45 participants that are $<$ 18 years old, at least 15
71 participants will be 12 to 17 years old, and at least 15 will be 6 to 11 years old. The 90 study participants
72 will also include a minimum of 15 pump users, 15 multiple daily injection of insulin (MDI) users, 15
73 CGM naïve users (may be pump or MDI users), and 15 experienced CGM users (may also be pump or
74 MDI users).
75

76 The subjects will be randomized to the order of the interventions based on a 1:1 ratio. Randomization
77 will not be stratified.
78

79 **4. Outcome Measures**

80 **4.1 Primary Efficacy Endpoint:**

81 Percent of CGM glucose sensor values < 70 mg/dL

83 **4.2 Secondary Efficacy Endpoints:**

84 *CGM Metrics*

85 Overall Glucose Control

86 1) Mean of CGM glucose sensor values

87 2) Percent of CGM glucose sensor values between 70 and 180 mg/dL (not inclusive of the
88 limits)

89 Hypoglycemia

90 3) Percent of CGM glucose sensor values < 60 mg/dL

91 4) Percent of CGM glucose sensor values < 50 mg/dL

92 5) Area over curve for CGM glucose sensor values < 70 mg/dL.

93 6) Low blood glucose index (LBGI).

94 7) Frequency of CGM-measured hypoglycemic events per week (see below)

95 Hyperglycemia

96 8) Percent of CGM glucose sensor values > 250 mg/dL

97 9) Percent of CGM glucose sensor values > 180 mg/dL

98 10) Area under curve for CGM glucose sensor values > 180 mg/dL.

99 11) High blood glucose index (HBGI)

101 **4.3 Calculation of CGM Metrics**

102 Each metric will be calculated for CGM sensor values over the entire 24-hour period.

103

104 Primary Outcome - % Time Below 70 mg/dL

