- Number of DKA events in the last 12 months
- Number of glucose tests per day
- Other non-insulin blood sugar control medications taken

For continuous variables, summary statistics appropriate to the distribution will be given. For discrete variables, number and percentage will be reported for each category.

11. Planned Interim Analyses

The purpose of the interim analysis is to re-estimate sample size in the case that the overall rate of hypoglycemia (% time below 70 mg/dL) in the control (SAP) arm is significantly less than what was assumed in the original sample size calculation. Only CGM data from baseline and the SAP arm will be used. The analyses will be masked to the PLGS data. No assessment of efficacy with the PLGS arm is to be made, and thus there will be no inflation of type 1 error rate.

With the planned sample size of 90, the original calculation estimated statistical power >99% to detect a 33% relative reduction assuming the control arm hypoglycemia is 4.0% using a two-tailed test with the type 1 error rate at 5%. The goal of this interim analysis is to assess whether the 4.0% assumption used in the original calculation was approximately correct, and if not whether the sample size needs to be modified. The interim analysis will be conducted when the 90th subject is enrolled into the screening phase. All partial data from all non-dropped subjects with either baseline or post-randomization CGM data will be included. Baseline CGM data will be taken as specified in Section 10, and all post-randomization data up to the final study period date will be included.

Study Stage Completed ^a	Rough Projection for # Subjects at Interim Analysis
CGM data from pre-randomization run-in ^b	N=90
Completed \geq 1 weeks of Period #1	N=45 (~22 or 23 randomized to control-first)
Completed Period #1	N=22 (~11 randomized to control-first)
Completed \geq 1 weeks into Period #2	N=0 (but possible if slower recruitment)
Completed Period #2	N=0 (but possible if slower recruitment)

^a Each row denotes a subset of subjects in the row above it.

^b Taken as specified in the table in section 10

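### Do 52 participants for 90% power, and power above 99% at 90, contradict the stated sample-size inputs?

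*Protocol*

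**What the plan says.** Protocol section 10.3 bases the calculation on data from an earlier external trial. It assumes a two-period crossover, "a 2-tailed test, a 33% relative reduction in 24-hour time <70 mg/dL", and "standard deviation of the paired differences = 3%, a type I error = 5%, and 90% power; a sample of 52". The control rate is not printed there. The same section continues: "With a sample size of 90 participants, the primary analysis will have 99% power".

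SAP section 11 supplies the control rate ("assuming the control arm hypoglycemia is 4.0" percent). For the 90 planned participants it puts the power above 99%, slightly stronger than the Protocol's figure, for the same relative effect and again with a two-sided test at the 5% level.

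Protocol section 10.11 and SAP section 11 then use the same 52 at the interim analysis. The adjusted sample size is 52 times 4%, divided by the estimated control-arm rate. Section 10.11 holds the result between 90 and 150 completers and describes the relation between sample size and control rate as only a rough proportionality.

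**The concern.** A reader who puts the printed inputs into the usual paired formula does not get 52. The difference is 0.33 × 4.0 = 1.32 percentage points, and with a standard deviation of 3 the answer is 55 by the normal formula or 57 by the paired t-test. At 90 participants the power comes out just under 99%, while the SAP says it is above 99%. Both figures miss in the favourable direction, which suggests that 52 was worked out for a control rate other than 4.0%.

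If so, the numerator 52 × 4% in the interim formula would be too small. The trial would be slow to go above 90 participants in the one situation the interim analysis is meant to catch, a control arm with little hypoglycaemia.

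**Working it through.** **Inputs.** Two-sided 5% test, 90% power, standard deviation of paired differences 3% and 33% relative reduction (Protocol 10.3); control rate 4.0% (SAP 11). Each participant contributes one pair. The formula, the test and the unrounded standard deviation are not stated.

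**Step 1: standard deviation exactly 3.00.** The normal formula is n = ((1.960 + 1.2816) × SD / difference)².

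- 33.0%: (3.2416 × 3 / 1.32)² = 54.3, so 55.
- One third: (3.2416 × 3 / 1.3333)² = 53.2, so 54.

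The paired t-test (noncentral t) adds two in each case.

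| Reading | N for 90% power | Power at 52 | Power at 90 |
|---|---|---|---|
| 33.0%, normal | 55 | 88.74% | 98.66% |
| 33.0%, t | 57 | 87.55% | 98.50% |
| One third, normal | 54 | 89.34% | 98.80% |
| One third, t | 56 | 88.18% | 98.65% |

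The closest reading is 2 participants from 52. All four power figures at 90 round to the Protocol's 99%.

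**Step 2: standard deviation known only as a whole number.** A printed 3% covers anything from 2.5 to 3.5. Keeping the control rate at 4.0%:

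| Reading | SD | N for 90% power | Power at 90 |
|---|---|---|---|
| 33.0%, normal | 2.92 | 51.4, so 52 | 99.01% |
| 33.0%, t | 2.88 | 52 | 99.04% |
| One third, normal | 2.94 | 51.1, so 52 | 99.04% |
| One third, t | 2.90 | 52 | 99.07% |

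For the first row, (3.2416 × 2.92 / 1.32)² = 51.4. Power at 90 is Φ(1.32 / 2.92 × √90 − 1.960) = Φ(2.329) = 99.01%. The t rows use n − 1 degrees of freedom. With n − 2, the 33.0% row needs 2.87 instead of 2.88, and the one-third row is unchanged.

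So 4.0%, 33%, an SD printed as 3%, 52 participants and power above 99% can all be true together.

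**Step 3: do the two printed results agree with each other?** If 52 participants give exactly 90% power, the normal formula gives power at 90 of Φ(3.2416 × √(90/52) − 1.960) = Φ(2.305) = 98.9%. The t-test gives 99.0%. The two figures are what a single calculation would produce, so both sitting slightly above the Step 1 values is one discrepancy, not two.

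**Step 4: effect on the interim formula.** With 52 the numerator is 52 × 4 = 208. It exceeds the floor of 90 only below 208 / 90 = 2.31%, and reaches the cap of 150 at 208 / 150 = 1.39%. With 57, the largest alternative, the numerator is 228 and the limits are 2.53% and 1.52%.

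| Estimated control rate | N with 52 | N with 54 to 57 |
|---|---|---|
| 3.0% or more | 90 | 90 |
| 2.5% | 90 | 90 to 92 |
| 2.0% | 104 | 108 to 114 |
| 1.5% | 139 | 144 to 150 |

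The widest gap is at 1.52%, where 57 gives 150 and 52 gives 208 / 1.52 = 136.8, so 137: a difference of 13. Outside roughly 1.4% to 2.5% the choice of constant changes nothing.

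**The case for a change.** The strongest case for the concern is that no reading of the inputs exactly as printed returns 52. At a standard deviation of 3.00, 52 falls short of 90% power in all four variants, and the SAP's claim of more than 99% at 90 would need 94 to 97 participants. A control rate near 4.17% with the t-test would also produce 52 and 99.0% power at 90. If that rate was used, pairing 52 with 4% in the interim formula is wrong, and it is wrong at the low control rates for which the re-estimation exists.

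The arithmetic stands, and so does the remark that section 10.3 cannot be reproduced on its own. The inference does not. A control rate of 4.17% is one candidate; a standard deviation of about 2.9 that was rounded to 3 is another, and it contradicts nothing in either document. The SAP says in terms that 4.0% was the assumed rate. The documents give no ground for preferring an explanation that contradicts them. Replacing 52 with 57, the most extreme of the four readings, could put a wrong constant into a correct formula.

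It is also not so that every adjusted sample size would be about 9% low. That figure requires 57 (57 / 52 = 1.096) and ignores the floor and the cap; with 54 the shortfall is under 4% (2 / 54 = 3.7%).

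**Conclusion.** The concern does not hold. With the standard deviation at exactly 3.00 the plan's 52 is 2 to 5 participants low and the SAP's power at 90 is overstated by 0.2 to 0.5 points. With a standard deviation that rounds to the printed 3%, both figures are exact at the stated 4.0% control rate. The Protocol's 99% is correct after rounding either way.

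This rests on the printed 3% being a rounded value, which the documents neither confirm nor exclude. If it were exactly 3.00, the consequence would still be small: the minimum of 90 completers is well above 52 to 57, power at 90 would be at least 98.5% under the stated assumptions, and the interim sample size would change by at most about 13, only for estimated control rates between about 1.4% and 2.5%.

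What remains is a matter of reporting: section 10.3 prints neither the control rate, nor the unrounded standard deviation, nor the test. That is missing detail, not an arithmetic error.

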10.9. Other Analyses

The following outcomes will be tabulated separately over 24-hour period, daytime, and nighttime where applicable:

- Insulin delivery including total insulin, basal insulin, and bolus insulin
- Frequency of insulin suspension events and duration of events, including individual suspensions and cumulative suspension time
- CGM glucose nadir during suspension events and peak within 2 hours after events
- The amount of CGM use in both 3-week periods.
- Percentage of time PLGS is active.

10.10. Baseline Descriptive Statistics

Baseline demographic and clinical characteristics of the study cohort including CGM metrics will be tabulated. For continuous variables, summary statistics appropriate to the distribution will be given. For discrete variables, number and percentage will be reported for each category.

10.11. Planned Interim Analyses

An interim analysis to re-estimate sample size will be conducted approximately when the 90th subject is enrolled into the screening phase of the study. The objective is to assess whether the observed rate of hypoglycemia in the control arm matches the value assumed in the original sample size calculation.

A longitudinal regression model will be fit using CGM data from SAP use during run-in and available outcome data from the control arm during Period 1 (for subjects randomized to control-first) and during Period 2 (for subjects randomized to control-second). The dependent variable will be CGM measured hypoglycemia to match the primary outcome described above. This model will be used to estimate the amount of hypoglycemia in the control arm.

The required sample size is roughly proportional to the amount of hypoglycemia in the control arm. The adjusted sample size will therefore be calculated as:

$$52*4\% / \text{estimated hypoglycemia rate in control arm}$$

where the estimated rate in the denominator is calculated from the regression model described above. This new sample size would be restricted to be a minimum of N=90 and a maximum of N=150 subjects completing the crossover trial with sufficient data to include in the primary analysis. If conditional power is <20% even with a sample size of N=150, the study may be stopped and limited to the subjects who have already been randomized (N not to be less than approximately 100).

1223
1224 Simulations show that basing the sample size on the estimated control arm rate in this manner does not
1225 materially inflate the type 1 error rate.
1226
1227 **10.12. Sub-Group Analyses**
1228 The primary outcome will be tabulated by:
1229

- age
- diabetes duration
- baseline HbA1c
- baseline CGM hypoglycemia

1230
1231
1232
1233
1234 These analyses are considered exploratory and are not being evaluated as independent hypothesis tests.
1235
1236 **10.13. Multiple Comparison/Multiplicity**
1237 The primary analysis involves a simple treatment arm comparison for a single outcome measure so no
1238 correction for multiple comparisons will be performed.
1239
1240 For the secondary analyses described above, the false discovery rate will be controlled using the
1241 adaptive Benjamini-Hochberg procedure for multiple comparisons. Note that this procedure can
1242 handle correlated outcome metrics and does not assume independent hypothesis tests.
1243
1244 **10.14. Exploratory Analyses**
1245 No additional exploratory analyses are planned.

1246 CHAPTER 11: DATA COLLECTION AND MONITORING

1247 1248 **11.1. Case Report Forms and Device Data**

1249 The main study data are collected through a combination of electronic case report forms (CRFs) and
1250 electronic device data files obtained from the study software and individual hardware components.
1251 These electronic device files and electronic CRFs from the study website are considered the primary
1252 source documentation.

1253 When data are directly collected in electronic case report forms, this will be considered the source data.
1254 Each participating site will maintain appropriate medical and research records for this trial, in
1255 compliance with ICH E6 and regulatory and institutional requirements for the protection of
1256 confidentiality of participants.

1257 1258 **11.2. Study Records Retention**

1259 Study documents should be retained for a minimum of 2 years after the last approval of a marketing
1260 application in an ICH region and until there are no pending or contemplated marketing applications in
1261 an ICH region or until at least 2 years have elapsed since the formal discontinuation of clinical
1262 development of the investigational product. These documents should be retained for a longer period,
1263 however, if required by local regulations. No records will be destroyed without the written consent of
1264 the sponsor, if applicable. It is the responsibility of the sponsor to inform the investigator when these
1265 documents no longer need to be retained.

1266 1267 **11.3. Quality Assurance and Monitoring**

1268 Designated personnel from the Coordinating Center will be responsible for maintaining quality
1269 assurance (QA) and quality control (QC) systems to ensure that the clinical portion of the trial is
1270 conducted and data are generated, documented and reported in compliance with the protocol, Good
1271 Clinical Practice (GCP) and the applicable regulatory requirements. Adverse events will be prioritized
1272 for monitoring.

1273 1274 A risk-based monitoring (RBM) plan will be developed and revised as needed during the course of the
1275 study, consistent with the FDA “Guidance for Industry Oversight of Clinical Investigations — A Risk-
1276 Based Approach to Monitoring” (August 2013). Study conduct and monitoring will conform with 21
1277 Code of Federal Regulations (CFR) 812.

1278 1279 The data of most importance for monitoring at the site are participant eligibility and adverse events.
1280 Therefore, the RBM plan will focus on these areas. As much as possible, remote monitoring will be
1281 performed in real-time with on-site monitoring performed to evaluate the verity and completeness of
1282 the key site data. Elements of the RBM may include:

- 1283 1284 • Qualification assessment, training, and certification for sites and site personnel
- 1285 1286 • Oversight of Institutional Review Board (IRB) coverage and informed consent procedures
- 1287 1288 • Central (remote) data monitoring: validation of data entry, data edits/audit trail, protocol review
of entered data and edits, statistical monitoring, study closeout
- 1289 1290 • On-site monitoring (site visits): source data verification, site visit report
- 1291 1292 • Agent/Device accountability
- Communications with site staff
- Patient retention and visit completion

1293 • Quality control reports
1294 • Management of noncompliance
1295 • Documenting monitoring activities
1296 • Adverse event reporting and monitoring
1297

1298 Coordinating Center representatives or their designees may visit the study facilities at any time in order
1299 to maintain current and personal knowledge of the study through review of the records, comparison
1300 with source documents, observation and discussion of the conduct and progress of the study.

1301

1302 **11.4. Protocol Deviations**

1303 A protocol deviation is any noncompliance with the clinical trial protocol, GCP, or procedure
1304 requirements. The noncompliance may be either on the part of the participant, the investigator, or the
1305 study site staff. As a result of deviations, corrective actions are to be developed by the site and
1306 implemented promptly.

1307

1308 The site PI/study staff is responsible for knowing and adhering to their IRB requirements. Further
1309 details about the handling of protocol deviations will be included in the monitoring plan.

1310 **CHAPTER 12: ETHICS AND PROTECTION OF HUMAN PARTICIPANTS**

1311 **12.1. Ethical Standard**

1313 The investigator will ensure that this study is conducted in full conformity with Regulations for
1314 the Protection of Human Participants of Research codified in 45 CFR Part 46, 21 CFR Part 50,
1315 21 CFR Part 56, and/or the ICH E6.

1316 **12.2. Institutional Review Boards**

1318 The protocol, informed consent form(s), recruitment materials, and all participant materials will
1319 be submitted to the IRB for review and approval. Approval of both the protocol and the consent
1320 form must be obtained before any participant is enrolled. Any amendment to the protocol will
1321 require review and may require approval by the IRB before the changes are implemented to the
1322 study. All changes to the consent form will be IRB approved; a determination will be made
1323 regarding whether previously consented participants need to be re-consented.

1324 **12.3. Informed Consent Process**

1325 **12.3.1. Consent Procedures and Documentation**

1327 Informed consent is a process that is initiated prior to the individual's agreeing to participate in
1328 the study and continues throughout the individual's study participation. Extensive discussion of
1329 risks and possible benefits of participation will be provided to the participants and their families.
1330 Consent forms will be IRB-approved and the participant will be asked to read and review the
1331 document. The investigator will explain the research study to the participant and answer any
1332 questions that may arise. All participants will receive a verbal explanation in terms suited to their
1333 comprehension of the purposes, procedures, and potential risks of the study and of their rights as
1334 research participants. Participants will have the opportunity to carefully review the written
1335 consent form and ask questions prior to signing.

1337 The participants should have the opportunity to discuss the study with their surrogates or think
1338 about it prior to agreeing to participate. The participant will sign the informed consent document
1339 prior to any procedures being done specifically for the study. The participants may withdraw
1340 consent at any time throughout the course of the trial. A copy of the informed consent document
1341 will be given to the participants for their records. The rights and welfare of the participants will
1342 be protected by emphasizing to them that the quality of their medical care will not be adversely
1343 affected if they decline to participate in this study.

1344 **12.3.2. Participant and Data Confidentiality**

1346 Participant confidentiality is strictly held in trust by the participating investigators, their staff,
1347 and the sponsor(s) and their agents. This confidentiality is extended to cover testing of biological
1348 samples in addition to the clinical information relating to participants. Therefore, the study
1349 protocol, documentation, data, and all other information generated will be held in strict
1350 confidence. No information concerning the study or the data will be released to any unauthorized
1351 third party without prior written approval of the sponsor.

1353 The study monitor, other authorized representatives of the sponsor, representatives of the IRB or
1354 device company supplying study product may inspect all documents and records required to be
1355 maintained by the investigator, including but not limited to, medical records (office, clinic, or

1356 hospital) and pharmacy records for the participants in this study. The clinical study site will
1357 permit access to such records.

1358

1359 The study participant's contact information will be securely stored at each clinical site for
1360 internal use during the study. At the end of the study, all records will continue to be kept in a
1361 secure location for as long a period as dictated by local IRB and Institutional regulations.

1362

1363 Study participant research data, which is for purposes of statistical analysis and scientific
1364 reporting, will be transmitted to and stored at the Jaeb Center for Health Research. This will not
1365 include the participant's contact or identifying information. Rather, individual participants and
1366 their research data will be identified by a unique study identification number. The study data
1367 entry and study management systems used by clinical sites and by Jaeb Center for Health
1368 Research staff will be secured and password protected. At the end of the study, all study
1369 databases will be de-identified and archived at the Jaeb Center for Health Research.

1370

1371 **12.3.3. Future Use of Stored Specimens**

1372 Not applicable

1373

1374 **CHAPTER 13: INVESTIGATOR AND SPONSOR OBLIGATIONS**

1375 **13.1. Role of Sponsor**

1376 As the study sponsor of this clinical trial, Tandem Diabetes Care, Inc. has the overall responsibility for
1377 the conduct of the study, including the assurance that the study meets regulatory requirements and is
1378 conducted according to Good Clinical Practice.

1380 **13.2. Medical Supervision and Investigator Responsibility**

1381 Medical supervision is the responsibility of the investigator named on the Investigator Agreement. The
1382 investigator may delegate day-to-day activities to a sub-investigator or study staff member, but retains
1383 overall responsibility for ensuring that the study is conducted properly and in accordance with the
1384 study protocol. A delegation list is to be maintained that includes all qualified persons to whom the
1385 investigator may delegate significant study-related duties. The investigator is responsible for ensuring
1386 that drugs and devices are available for treating possible medical emergencies, or that emergency
1387 medical facilities are available and accessible. The investigator is responsible for ensuring that the
1388 study is conducted according to Good Clinical Practice (GCP), other applicable regulatory guidelines,
1389 and sound medical practices.

1391 **13.3. Study Initiation and Sponsor Discontinuation**

1392 Prior to initiation of the study, the investigator must provide the Sponsor or designee with the
1393 following documents (copies of which must be maintained by the investigator):

- 1394 • Completed and signed original Investigator Agreement
- 1395 • Current curriculum vitae, signed and dated; also required is a state license for the investigator
1396 and for other medically qualified sub-investigators
- 1397 • Completed Financial Disclosure information
- 1398 • Signed copy of the Institutional Review Board (IRB) approval letter that lists the approved
1399 items
- 1400 • List of the IRB members who voted on the approval, including their specialty and affiliation, or
1401 the IRB assurance numbers if the roster cannot be obtained
- 1402 • Copy of the IRB-approved informed consent
- 1403 • Copy of the IRB-approved Authorization to Use and Disclose Protected Health Information
1404 form, consistent with the Health Insurance Portability and Accountability Act of 1996 (HIPAA)
1405 legislation (if separate from the informed consent form)

1406 Upon receipt of all necessary paperwork, the Sponsor or designee will arrange for all study material to
1407 be delivered to the clinical study site. The Sponsor or designee will conduct an initiation conference
1408 call or visit to orient and provide in-depth training for all personnel expected to be involved in the
1409 study. Study protocol procedures, instruction for data capture, and overall responsibilities, including
1410 device accountability and study file maintenance, will be reviewed.

1411 The Sponsor has the right to terminate the study for any of the following reasons:

- 1412 • Non-adherence to the protocol
- 1413 • Unavailability of the investigator or the study personnel to the sponsor's monitoring personnel
1414 (or their designee)
- 1415 • Inability to recruit the expected participant population
- 1416 • Other administrative reasons

1421 Throughout the course of the study, the investigator is to make a reasonable effort to maintain the
1422 enrollment rate that was agreed upon with the Sponsor. The investigator will also make a reasonable
1423 effort to enroll appropriate participants. The sponsor may elect to terminate the study at a given site if
1424 the enrollment rate lags or if significant numbers of non-evaluable participants are enrolled.
1425
1426

1427 CHAPTER 14: APPENDIX A – EXTENSION PHASE

1428 1429 **Introduction**

1430 The Tandem PLGS Pivotal Trial is being extended to allow interested trial participants to continue to
1431 use the Tandem PLGS pump system after completion of the main trial.

1432 1433 **Study Design**

1434 All participants will be assigned the Tandem PLGS pump and will return to the clinic approximately
1435 every 13 weeks (± 2 weeks). The Extension Phase will continue until the system is commercially
1436 available or two years after the initial regulatory approval date, whichever comes first.

1437 1438 **Participant Eligibility and Informed Consent**

1439 Participants who completed the PLGS Pivotal Trial within the previous 6 months will be eligible for
1440 the Extension Phase.

1441 1442 Study sites will inform the participants regarding the Extension Phase. Interested participants,
1443 parents/guardians, or both will sign new consent/assent forms.

1444 1445 **Extension Phase Procedures**

1446 At the initial visit after the consent (and assent if applicable) is signed, the participant will be provided
1447 with study supplies and device training as needed. Study supplies include: study pump and related
1448 supplies, study CGM and related supplies, and study blood glucose and ketone meters and test strips.

1449 1450 The home procedures will be the same as described in sections 5.3 and 5.4. Device use will be as
1451 described in Chapter 6.

1452 1453 At each 13-week (± 2 weeks) follow-up visit and for the final visit, device data will be uploaded. The
1454 occurrence of adverse events and device issues will be solicited, as well as any new medications or
1455 medical conditions since the previous visit. Other testing and changes in diabetes management will be
